2.4 Level of significance

The level of significance that will be used in all the statistical analyses is 5%, two-sided. However, 95% confidence intervals will be preferred to p -values in the final report.

2.5 Sample size

This section combines the initial power calculations with the ones amended after the Milestone 1 review in January 2018, when the study design was changed from CLR only to CLR and PLR. A more detailed explanation on sample size calculations and variable follow-up periods is available here:

[G:\EMS\CPTU\BEST3\Section 26 STATISTICS\26.3 Power calculations\Sample size \(following Amendment 6\)\BEST3_Sample_size.pdf](G:\EMS\CPTU\BEST3\Section 26 STATISTICS\26.3 Power calculations\Sample size (following Amendment 6)\BEST3_Sample_size.pdf)

2.5.1 Changes to study design after Milestone 1 review

The BEST3 study was planned as a cluster randomised trial stratified by practice size in order to achieve a reduction in the variance of the estimated treatment effect. This is done by reducing the coefficient of variation of the cluster size within strata. This gives a higher power to the study.

In the initial stage of the study, uptake of the Cytosponge™ was anticipated to be 50%. A lower uptake than anticipated was the main reason why a change in study design was needed – the sample size for a CLR trial with uptake lower than 50% would have been too large to be sustainable for the study. Given the substantial impact to the power of the trial, it was proposed that an additional PLR randomisation design be added to the trial. The reason for the lower than anticipated participation and for why we considered it important to adapt the design to take account of it is explained below.

Originally, the trial was envisaged as recruiting patients presenting to their GPs with (incident) symptoms of reflux. For this reason, we: (1) felt that GP-practice-level randomisation was essential; and (2) assumed that with the personal endorsement of the GP and the fact that patients were essentially asking their GP for help with their reflux, acceptance of the offer of a Cytosponge™ test would be high (50%).

For practical reasons (related to trial delivery), BEST3 has been randomising “prevalent” patients, i.e. practices identify patients who have drug prescription records indicating reflux and invite them (or not, depending on randomisation) all at once. Identification using prescribing history rather than at the presenting appointment has resulted in a much lower uptake than anticipated (approximately 27%). (Patients may have been on reflux medication for many years without recently having had symptoms or consulted with their GP.) We still believe that, were the Cytosponge™ to be offered by GPs to patients presenting with reflux as routine practice, the uptake would be much higher.

To obtain sufficient power without greatly expanding the number of participants and practices required, we adapted the design to allow PLR. Practices already set up or trained to take part in the CLR continued with this randomisation method. Practices engaged at a later date would use individual randomisation.

3000 in an individually randomised trial. As we increase the number of invitees per cluster (i.e. GP practice), the VIF increases, too. In simple terms, there are diminishing returns.

The sample size calculated above would have initially been multiplied by the **variance inflation factor** (VIF). We estimated the VIF as follows:

$$VIF = 1 + \left(\left(\frac{k-1}{k} CV^2 + 1 \right) mean - 1 \right) ICC$$

where:

- k , the number of practices in the group
- $mean$, the average size of the practices in the group
- CV^2 , the square of the coefficient of variation of the number of patients per practice, which was in turn calculated by dividing the standard deviation by the mean
- ICC , the intra-class correlation coefficient

The **intra-class correlation** (of the proportion of patients with BE) was assumed to be 0.025.

The VIF can be calculated overall or by stratum. After the Milestone 1 review, practices in the cluster-randomised group were divided into two groups: practices whose enrolment and size (i.e. recruitment numbers) was confirmed, and practices whose enrolment was expected and whose size was estimated. For both groups, practices were grouped into strata based on their size: 50-65, 66-90, 91-125, 126-175, 176-225. With data available on 9th January, we estimated the VIF in each stratum to be: 2.44, 2.96, 3.59, 4.77, and 5.91, respectively, for the confirmed practices. We also estimated VIFs for the projected practices and anticipated 11,816 patients in total from 100 practices contributing the equivalent of 2924 individually randomised patients (1724 “confirmed”, 1200 projected).

The required **sample size** in a PLR setting was calculated above to be **6764**. The equivalent confirmed and projected sizes are to be subtracted to this number, and the result is the number of patients that needed to be recruited in the **PLR group**:

$$6764 - 1724 - 1200 = \mathbf{3840}$$

and the total sample size overall was 15,656 (11,816 + 3,840) participants.

During the trial, recruitment numbers were checked several times and the size of the PLR group was adjusted accordingly.

As of 13th June 2019, **7844** participants were recruited in the **CLR group** (equivalent size: 2120) and **5390** in the **PLR group** after the initial 14-day opt-out period, for a total of 13,234 participants. Note that the CLR practices eventually recruited fewer patients than expected at the time of the Milestone 1 review, and that implied a higher recruitment in the PLR group, whose participants contribute more to the power of the study.

The table below shows a range of possible values for our sample size depending on how we adjust the estimate of our parameters.

	BE prevalence	Cytosponge™ TFF3 sensitivity	Endoscopy in usual care arm (over 12 months)	BE prevalence in patients getting routine endoscopy	Uptake of Cytosponge™	Intra-class correlation coefficient	Sample size if only individual randomisation	Equivalent sample size accounted for by cluster randomisation (11,816 patients in 100 practices)	Remaining sample size for PLR group
Our assumptions	4.0%	85%	10%	6%	27%	0.025	6764	2924	3840
Varying assumptions	3.9%	85%	10%	6%	27%	0.025	7098	2924	4174
	4.1%	85%	10%	6%	27%	0.025	6456	2924	3532
	4.0%	84%	10%	6%	27%	0.025	6894	2924	3970
	4.0%	86%	10%	6%	27%	0.025	6638	2924	3714
	4.0%	85%	9%	6%	27%	0.025	5658	2924	2734
	4.0%	85%	11%	6%	27%	0.025	8176	2924	5252
	4.0%	85%	10%	5%	27%	0.025	5048	2924	2124
	4.0%	85%	10%	7%	27%	0.025	9344	2924	6420
	4.0%	85%	10%	6%	26%	0.025	7190	2924	4266
	4.0%	85%	10%	6%	28%	0.025	6380	2924	3456
	4.0%	85%	10%	6%	27%	0.024	6764	3012	3752
	4.0%	85%	10%	6%	27%	0.026	6764	2840	3924

2.5.3 Lower uptake of the Cytosponge™ invitation

In the updated sample size calculations of Milestone 1, uptake of the Cytosponge™ invitation was expected to be 27%. However, in the data available in June 2019, uptake was closer to 24.0%, which would be equivalent to 84% power according to the same assumptions as in the section above. At the same time, it should be noted that currently we are expecting to recruit 746 patients more than needed by our sample size calculations, so that would raise the power of the study to 87%.

The following table shows how the power of the study varies by keeping the same sample size and changing some of the initial assumptions.

Uptake	Prevalence of BE in eligible population	Prevalence of BE in those referred to endoscopy	Sample size (with 90% power)	Power with n = 6764
27.0%	0.04	0.06	6768	90%
24.0%	0.04	0.06	8260	83%
24.0%	0.05	0.06	5388	95%
24.0%	0.04	0.05	10126	75%
24.0%	0.05	0.05	6246	92%
23.0%	0.04	0.06	8886	81%
22.0%	0.04	0.06	9350	79%
21.0%	0.04	0.06	10126	75%

2.5.4 Variable follow-up periods

Because of delays in the implementation of the change of study design (from CLR to CLR with additional PLR group), it was decided that participants/practices could have

a follow-up longer than 12 months to compensate for participants/practices who will have a follow-up shorter than 12 months due to time constraints.

Different practices will have different follow-ups as long as the **weighted average follow-up** for the study will be greater than 12 months, as shown by the following formula:

$$\text{avg}_{\text{FU}} = \frac{\sum_{i=1}^P F_i M_i + \sum_{j=1}^Q F_j N_j}{\sum_{i=1}^P M_i + \sum_{j=1}^Q N_j} \geq 12$$

where F_i, F_j are the different lengths of follow-up (in months) for each different group, M_i are the numbers of patients with different follow-ups in the CLR group in 'equivalent size' terms, N_j are the numbers of patients with different follow-ups in the PLR group, $\sum_{i=1}^P M_i$ is the total size (in 'equivalent' terms) of the CLR group, and $\sum_{j=1}^Q N_j$ is the total size of the PLR group.

According to our current projections, all practices will have between 8 and 18 months of follow-up. The end date of follow-up will be when a site performs their local coded search; it will therefore be taken from the Coded Search case report form (CRF).

Note: in case a weighted average follow-up of 12 months or more could not be guaranteed, the power of the study would be less than 90%. The following table illustrates the potential loss in power with shorter follow-up:

Total average follow-up (months)	Factor by which to inflate sample size
9	1.24
9.5	1.18
10	1.13
10.5	1.09
11	1.06
11.5	1.03

A detailed explanation on how to calculate the factors by which to inflate the sample size is available here:

[G:\EMS\CPTU\BEST3\Section 26 STATISTICS\26.3 Power calculations\Sample size \(following Amendment 6\)\BEST3_Sample size.pdf](G:\EMS\CPTU\BEST3\Section 26 STATISTICS\26.3 Power calculations\Sample size (following Amendment 6)\BEST3_Sample size.pdf)

2.5.5 Randomisation algorithm

For the CLR group, practices were randomised to either the intervention or the usual care arm. This was done using a randomisation algorithm that stratified by practice size.

For the PLR group, a single randomisation list was created using block randomisation, allowing for 40 practices of 250 patients each to be randomised, for a total of slightly more than 10,000 potential patients (depending on the size of the last randomisation block). A further step of randomisation was introduced to decide the order in which the practices would be assigned to the list. In January 2009, in order to allow for more practices to be enrolled into the study, a new randomisation list with 10 more practices of 250 patients each was created.

More details on the randomisation algorithms and validations can be found here:

BEST3 SOP 008 – BEST3 Statistical Analysis Plan v1.0. [If this SAP has been printed or saved electronically, please check Sharepoint to ensure this version is the most up-to-date.](#)

CPTU Template Creating and Revising SOPs and other Guidelines v11.0 05/Jul/2019

3. General analysis definitions

3.1 Study periods

Follow-up periods will be **variable** as shown in Section 2.5.4.

3.2 Study populations

3.2.1 Intention-to-treat population

The intention-to-treat (ITT) population will include all participants enrolled into the study. The following participants will be *included* in the ITT analysis:

- Deceased patients:
BE status at death will be used as their BE status at the end of the trial.
- Study subjects that moved away from a practice:
We are unlikely to know how long such patients were followed because we only receive aggregate data regarding most patients. For this reason, we will treat them as if they were followed for the same duration as other patients in that practice unless we know when they moved, in which case their follow-up will be treated as censored at that time.
- Participants lost to follow-up due to local information governance restrictions:
If we have no follow-up on all patients in a particular practice, that practice will effectively be excluded. The fact that this has happened will be noted. Individuals with a Cytosponge™ test will still be included in the intervention-arm only results assuming that BE found as a result of a positive Cytosponge™ will have been recorded. If a patient withdraws consent for their data to be used for research purposes ('Type 2' objection), they will be excluded.

As detailed data are only available for consented patients in the intervention arm, for all patients we assume a follow-up equal to the follow-up of their practice, with the exception of any known participants invited to a research endoscopy before the end of their follow-up period. However, it should be noted that IDs of participants with a BE/OGD/EAC/upper GI referral will be collected for both arms and available for the statistical analysis.

Subjects who opted out (Type 2 objection to their data being used, or explicitly writing to the study team asking for their data to be removed from the database) *after* being entered into the study (i.e. more than 14 days after receiving the trial introductory letter) will be *excluded* from the ITT analysis and any further analyses. The numbers of such patients in each arm will be reported.

Further exploratory epidemiological analyses to study the risk of BE according to baseline/demographics data may be detailed in a separate SAP for epidemiological analyses.

3.2.2 Per-protocol population

The per-protocol analysis will exclude any patient who we know should not have been randomised had the inclusion and exclusion criteria been followed precisely (for example, a patient outside of the age range). It may not be possible to identify individuals who do not meet the eligibility criteria in terms of acid-suppression use (see below).

The per-protocol analysis will also exclude any study subjects in the PLR group randomised to one study arm but erroneously assigned to the other and any participants who moved away before receiving the invitation to the test.

The per-protocol analysis will be performed for the primary endpoint only.

Using the number of case-note reviews available in a practice as the denominator, we will calculate the proportion of patients in a practice that have less than 6 months' worth of acid-suppressant medication prescriptions in the year preceding baseline. This proportion will be used as a threshold in our sensitivity analyses. However, practices recruited at the late stages of the Trial may not perform any additional case-note reviews other than for patients picked up by the local coded search of their clinical information system due to time restrictions. In order to overcome these issues, we plan to perform three different sensitivity analyses:

Sensitivity analysis 1: Exclude the practices we know have more than 20% of patients with less than 6 months' worth of acid-suppressant medication prescriptions as well as those practices for which this information is unknown i.e. there has been fewer than 20 patients whose notes have been reviewed manually.

Sensitivity analysis 2: Exclude only the practices we know have more than 20% of patients with less than 6 months' worth of acid-suppressant medication prescriptions.

Sensitivity analysis 3: Only exclude individual patients known to have had less than 6 months' worth of acid-suppressant medication prescriptions at randomisation.

Sensitivity analyses will be performed for the primary endpoint only.

Further investigations on this will compare the proportion of BEs detected in patients with less than 6 months' worth of acid-suppressant medication prescriptions vs the proportion of BEs detected in patients with more than 6 months' worth of such prescriptions. Because of the nature of the data (aggregated data + individual-level data for consented Cytosponge™ patients and patients who have their case-note reviewed), this exercise will only be performed with the individual-level data available.

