- Inadequacy rate = proportion of Cytosponge™ test results that are deemed insufficient/inadequate due to processing or technical failure, low-confidence negative (squamous cells only) or equivocal (squamous and glandular cells with equivocal TFF3 staining), to be reported with number of.
- Number and proportion of Cytosponge™ test results deemed insufficient/inadequate due to technical failure only
- Number and proportion of Cytosponge™ test results deemed low-confidence negative only
- Number and proportion of Cytosponge™ test results deemed equivocal only

The above measures will also be presented for first test only and for first and repeat test combined, excluding those patients receiving an inadequate test result but not attending their repeat test.

- 7) Endoscopy referral rates for 'adequate' test results and successful Cytosponge™ swallows:
- Proportion of positive Cytosponge™ patients out of all the ones with an adequate test result, both for first test only, and for first and repeat test combined
 - Proportion of positive Cytosponge™ patients out of all patients swallowing successfully a Cytosponge™ test, both for first test only, and for first and repeat test combined
- 8) Patient acceptability of Cytosponge™:

At first test:

- Number/proportion of patients invited who show interest
- Number/proportion of patients invited who receive screening phone call and how many of these are not eligible to have the test
- Willingness to have the test: number/proportion of patients invited who attend appointment
- Number/proportion of patients who fail to swallow
- Number of attempts to swallow per patient

At repeat test (in case of an 'inadequate' result at first test):

- Number/proportion of patients with an 'inadequate' first test result invited to a repeat test
- Number/proportion of patients with an 'inadequate' first test result interested or not interested in a repeat test
- Willingness to have repeat procedure: number/proportion of patients with an 'inadequate' test result who attend a second appointment
- Number/proportion of patients who fail to swallow
- Number of attempts to swallow per patient

All of these figures for first and repeat tests will be presented in a flowchart similar to the one used for the open Data Monitoring Committee (DMC) reports (see Section 10 for reference).

At baseline (before first test):

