3.4 Treatment assignment and treatment groups

Participants in the study were selected by an automated search in GP databases followed by a manual review of their records. All study subjects received an introductory letter to the study, allowing them 14 days to opt out of anonymised data collection. Following this, GP practices (for the CLR group) or participants (for the PLR group) were randomised to either receiving an invitation to the Cytosponge™ test or to usual care.

Non-responders of invitation to the Cytosponge™ were managed as were the patients in the usual care arm.

Participants with a positive Cytosponge™ result were invited to a **confirmatory endoscopy**. Negative Cytosponge™ patients were subsequently managed as were patients in the usual care arm.

Note: A small sample of patients in the usual care arm and negative Cytosponge™ patients were invited to a **research endoscopy** after the end of their follow-up period. The result of their research endoscopy is *not* part of the primary endpoint analysis. A handful of patients invited to the test were also invited to have a research

BEST3 SOP 008 – BEST3 Statistical Analysis Plan v1.0. [If this SAP has been printed or saved electronically, please check Sharepoint to ensure this version is the most up-to-date.](#)

endoscopy at the beginning of the roll-out of the procedure, but invitations to that group were stopped shortly thereafter, and any research endoscopy results in this group of patients will not be taken into account for any analyses.

4. Patient disposition

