4.1 Compliance to the Cytosponge™-TFF3 test

Compliance to test (intervention arm) will be defined on two aspects: attendance and successful swallows.

Participants will be provided with two opportunities to successfully swallow the device. A participant will be considered as having had the Cytosponge™ test if he or she has at least one successful swallow. Attenders will include patients who successfully swallow a sponge and those who present at their appointment but are not able to produce a successful swallow.

Study subjects successfully swallowing a Cytosponge™ may produce a sample deemed inadequate because of processing/technical failures or because the test result is considered to be low-confidence negative (squamous cells only) or equivocal (squamous and glandular cells with equivocal TFF3 staining). These patients will be invited to a repeat Cytosponge™ test.

The following numbers and proportions on compliance will feed into the Trial flowchart (see Figure 2):

- responders: overall, to first invitation letter only, to second invitation letter only
- interested and not interested (out of all responders)
- received screening phone call (out of interested): eligible, ineligible
- attenders and non-attenders/withdrawn (out of eligible)
- produced a successful swallow and unable to swallow (out of attenders)
- 'inadequate' samples (out of successful swallows) at first attempt and at repeat test: processing/technical failures, low-confidence negative (squamous cells only), equivocal (squamous and glandular cells with equivocal TFF3 staining)
- participants with 'inadequate' samples invited for a repeat test, attending the test, producing a successful swallow or unable to swallow
- 'adequate' samples (out of successful swallows) at first attempt, at repeat test, overall (i.e. only repeat test counts for participants having two tests) and in total (i.e. all tests counts): negative (squamous and glandular cells), low-confidence positive (squamous and glandular cells with IM), high-confidence positive (squamous and glandular cells with IM and cellular atypia)

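### Two per-protocol exclusions in SAP 3.2.2 rest on post-randomisation events or information that differ by arm: the mover rule tilts slightly towards the Cytosponge, the ineligibility rule in no predictable direction

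*SAP*

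**What the plan says.** Section 3.2.2 of the SAP defines three per-protocol exclusions, applied to the primary endpoint only:

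- Known ineligibility: "The per-protocol analysis will exclude any patient who we know should not have been randomised". The example given is a patient outside the age range.
- Misassignment: "any study subjects in the PLR group randomised to one study arm but erroneously assigned to the other".
- Moving: "any participants who moved away before receiving the invitation to the test".

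Section 3.4 says that practices or patients "were randomised to either receiving an invitation to the Cytosponge™ test or to usual care", so the invitation exists in one arm only.

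For movers in the ITT population, section 3.2.1 assigns the follow-up of the practice "unless we know when they moved, in which case their follow-up will be treated as censored at that time". It adds that the team will seldom know, since most data arrive in aggregate.

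On individual data, section 3.2.1 begins one statement with "As detailed data are only available for consented patients in the intervention arm". Section 5 lists what those who take up the invitation provide, including year of birth. Usual care has aggregate baseline tables, plus case-note reviews of a random sample or, at some sites, of everyone. Patients in either arm whom the coded search identifies should also be reviewed manually (section 2.3).

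**The concern.** A per-protocol set can keep the two arms comparable only if each exclusion could be applied to the same kind of person in either arm. The mover rule fails this test. Its reference event never happens in usual care, so it either never applies there or, read literally, would cover every usual-care mover. On the natural reading it takes people who were never invited or tested, and who therefore have at most about the usual-care yield, out of one denominator only.

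The ineligibility rule has a milder form of the problem. Who is known to be ineligible depends on how much is known about each person, and more is known about intervention attenders.

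The SAP guards against arm-dependent information elsewhere. Section 2.3 leaves out of the primary endpoint any Barrett's oesophagus (BE) known only to the study team, so that both arms are ascertained alike. Section 7.3.1 expects more late withdrawals in the intervention arm and adds a sensitivity analysis that puts them back. Section 3.2.2 has no such safeguard. At stake is whether the per-protocol result can be read beside the ITT result as a like-for-like comparison.

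**Working it through.** **Inputs (SAP 2.5.2).** Uptake 27%, BE prevalence 4%, Cytosponge sensitivity 85%, endoscopy in usual care 10%, BE among those referred 6%, endoscopy sensitivity 100%.

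**The plan's own figures.**
- Rate in tested patients: 0.04 × 0.85 + 0.15 × 0.10 × 0.06 = 0.0349.
- Rate in untested patients and in usual care: 0.10 × 0.06 × 1 = 0.006.
- Intervention arm: 0.27 × 0.0349 + 0.73 × 0.006 = 0.013803, the SAP's 1.38%.
- Two-sided 5%, 90% power, pooled variance: 3382 per arm, 6764 in total, as stated.
- Planned ratio: 0.013803 / 0.006 = 2.30.

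**One-sided exclusion.** Remove a share f of the intervention arm only, with BE rate r among those removed:

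ratio = (0.013803 − f × r) / (1 − f) / 0.006

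The SAP gives no number of exclusions, so f = 1% and 2% are assumptions.

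| f | r = 0 (no BE found) | r = 0.6% (untested) | r = 3.49% (tested) |
|---|---|---|---|
| 1% | 2.32 | 2.31 | 2.26 |
| 2% | 2.35 | 2.33 | 2.23 |

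Example: f = 2%, r = 0 gives 0.013803 / 0.98 = 0.01408, and 0.01408 / 0.006 = 2.35.

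The first two result columns describe movers who were never tested. If the test had no effect, r = 0 would give ratios of 1.01 and 1.02. The two-sided rejection rate at 3382 per arm would then be 5.01% and 5.05%.

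**Allowing for person-time.** The primary analysis uses person-years, and a mover with a known date is already censored. Let g be the fraction of full follow-up that such a mover contributes, with no BE. Dropping the mover from the per-protocol set multiplies the ratio by 1 + f × g / (1 − f).
- g = 1 (not censored), f = 2%: 1.020, as in the table.
- g = 1/12 (assumed: one month out of twelve), f = 2%: 1 + 0.02 × 0.0833 / 0.98 = 1.002.

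Where the date is known, the exclusion itself therefore does little. But if dates were known in the intervention arm only, the censoring would already shift the ITT ratio by 1 / (1 − f × (1 − g)) = 1 / (1 − 0.02 × 0.9167) = 1.019, from 2.30 to 2.34. The asymmetry then sits in ITT instead.

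**Direction of the ineligibility rule.** Suppose a share q of those excluded were tested and the rest were not. The ratio is unchanged when the mean BE rate in the excluded equals 0.013803:
- Untested at 0.6%: q = (0.013803 − 0.006) / (0.0349 − 0.006) = 0.27.
- Untested at 0: q = 0.013803 / 0.0349 = 0.40.

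Above these shares the exclusion works against the Cytosponge; below them, in its favour. Attenders supply the year of birth, so a high share of tested patients is plausible.

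**The case against.** The strongest case on the other side has five parts.

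- *Known movers are already censored.* This stands as far as it goes: the headcount figures are upper values, and the extra effect of exclusion on a censored mover is negligible. It does not restore symmetry. A usual-care mover with an unknown date keeps full practice follow-up. Early moves are probably more often noticed in the arm that is being contacted, although the SAP does not say so.
- *Exclusions can arise in both arms.* This stands. Misassignment applies to either arm, and case-note reviews and coded-search identifiers exist in both. A reader might infer that the per-protocol exclusions can be made only in the intervention arm; the SAP does not support that.
- *The screening call is not an exclusion criterion.* This stands. Section 2.3 reports "Number/proportion of patients invited who receive screening phone call and how many of these are not eligible to have the test", and section 4.1 lists "received screening phone call (out of interested): eligible, ineligible". Both concern having the test. Section 3.2.2 concerns who should have been randomised, and nothing in the SAP links the two.
- *Anchoring to the start of follow-up would exclude almost no randomised mover.* Probably true, since that date falls about when the opt-out period ends and randomisation follows. It is a reason to accept deletion of the rule as an equal alternative, not to keep the present rule.
- *The analysis is supplementary.* This stands: no decision depends on the per-protocol result, and ITT membership does not change.

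**Conclusion.** The point holds in a limited form. The mover rule has no usual-care counterpart and, as written, biases the per-protocol ratio slightly towards the Cytosponge: from 2.30 to about 2.31 to 2.35 if 1% to 2% of the intervention arm is removed with full follow-up, and by less where the move is censored. This rests on the SAP's design rates, on an assumed share removed, and on usual-care movers being retained.

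The ineligibility rule depends on information that is richer for intervention attenders than for usual care. Its direction is not predictable: excluding tested patients lowers the ratio (2.26 at 1%, 2.23 at 2%), and exclusions found by review in usual care may move that arm's rate too.

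A reader might infer that the whole per-protocol analysis is biased towards the Cytosponge, or that the inflation is large. The SAP supports neither. The direction is secure for the mover rule only, and nothing in the document suggests that more than a small share would be excluded.

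**What to change.** 1. Tie the mover exclusion to the start of follow-up that section 7.1.1 already defines for both arms (introductory letter plus 15 days), or delete it.
2. Limit exclusions for known ineligibility to information obtained in the same way in both arms at or before randomisation, such as the eligibility search and its manual record review (section 3.4). State that findings from the screening call or the attenders' baseline forms do not lead to per-protocol exclusion.
3. In section 3.2.1, censor at a known moving date only when it comes from a source searched equally in both arms. Otherwise use the practice follow-up.
4. Report per-protocol exclusions by arm and reason.

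The cost is SAP wording and one extra table; no new data are needed. The downside is that a few intervention patients known to be ineligible or to have moved remain in the per-protocol set.
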